10.2 External Placebo Assumptions

In order to derive robust external placebo assumptions for the co-primary and ranked secondary endpoints, a thorough literature search of placebo-controlled clinical studies in subjects with moderate to severe UC who had failed conventional therapy was performed. Studies M06-826 and M06-827 were the only available data sources with PMS data at Week 8. Studies GEMINI 1 and OCTAVE Sustain were the only studies with a similar subject population (i.e., failure or intolerance to prior corticosteroids or IMMs), study design (i.e., randomized withdrawal), and endpoint definitions for derivation of external placebo rates for the Week 52 endpoints in Study M11-290.

For all co-primary and ranked secondary endpoints where available, separate estimates for anti-TNF naïve placebo patients and anti-TNF experienced placebo patients were derived as described by endpoint below. The estimates for anti-TNF naïve placebo patients and anti-TNF experienced placebo patients were then combined as a weighted mean according to the assumed proportion of anti-TNF naïve and experienced subjects as per the Study M11-290 protocol, i.e., $0.75 \times \text{rate}$ in anti-TNF naïve $+ 0.25 \times \text{rate}$ in anti-TNF experienced subjects. To be conservative, the upper limit of the 95% CI for the weighted mean was used as the external placebo assumption.

For PMS remission at Week 8: A remission rate of anti-TNF naïve placebo patients was estimated using logistic regression with anti-TNF naïve placebo patients from Studies M06-826 and M06-827 and study as a fixed effect, in order to weight the studies according to their sample sizes. Anti-TNF experienced placebo patients were only available in Study M06-827, so the remission rate from this study only was used as remission rate for anti-TNF experienced placebo patients.

For Mayo Score remission and mucosal healing at Week 52 in Week 8 responders per PMS, as well as for Mayo Score remission at Week 52 in Week 8 remitters per PMS: Separate remission rates of anti-TNF naïve and anti-TNF experienced placebo patients were estimated using separate logistic regression models with anti-TNF naïve placebo patients and anti-TNF experienced placebo patients, respectively, from GEMINI 1 and

OCTAVE Sustain and study as a fixed effect, in order to weight the studies according to their sample sizes.

For Mayo Score response: Week 52 in Week 8 responders per PMS: Results were not available by anti-TNF naïve versus anti-TNF experienced placebo patients, so the overall response rates in placebo subjects from GEMINI 1 and OCTAVE Sustain were combined via logistic regression with study as a fixed effect, in order to weight the studies according to their sample sizes.

For steroid-free remission per Mayo Score at Week 52 in Week 8 responders per PMS with corticosteroids at Baseline: Only data from GEMINI 1 was available. Rates of anti-TNF naïve and anti-TNF experienced placebo patients from GEMINI 1 were combined to a weighted mean $(0.75 \times \text{rate in anti-TNF naïve} + 0.25 \times \text{rate in anti-TNF experienced}$ subjects) and the upper bound of the 95% CI for the weighted mean was used.

[figure not shown]
External Placebo Assumptions for Co-Primary and Ranked Secondary Efficacy Endpoints

Endpoint	External Placebo Rate (95% CI Upper Limit from Meta-Analysis)
Week 8 PMS Remission	19.83%
Week 52 FMS Remission in Week 8 Responders per PMS	18.37%
Week 52 FMS Response in Week 8 Responders per PMS	26.10%
Week 52 Mucosal Healing in Week 8 Responders per PMS	22.03%
Week 52 FMS Remission in Week 8 Remitters per PMS	14.79%
Week 52 FMS Remission in Week 8 Responders per PMS with CS at Baseline and Discontinued CS prior to Week 52	24.08%

FMS = Full Mayo Score; PMS = Partial Mayo Score; CS = Corticosteroids

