The primary efficacy analysis for the co-primary endpoint at Week 8 is based on external placebo comparison identified from an ongoing meta-analysis of relevant publically available clinical trials. In order to demonstrate efficacy of adalimumab at Week 8 in the pediatric population, the lower limit of the 95% CI for the remission rate per PMS in the high induction dose group is required to be higher than the upper limit of the 95% CI of the remission rate of external placebo (assumptions based on the adult UC Studies M06-826 and M06-827 are shown in the following table for illustrative purposes only).

The primary efficacy analysis for the co-primary endpoint at Week 52 is based on the comparison of the high maintenance dose group versus external placebo using the same efficacy criterion described above.

Placebo Data from Adult UC Studies

Endpoint	Placebo Subjects by Prior Anti-TNF Status			
	Experienced n/N (%)	Naïve n/N (%)	Weighted Average for 25% Experienced +75% Naïve	
			%	95% CI Upper Limit
Week 8 Partial Mayo Score Remission (Pooled Studies M06-826 and M06-827 IAS-E set ^a)	15/101 (14.9%)	61/367 (16.6%)	16.18%	19.52%
Week 52 Mayo Score Remission (Study M06-827 ITT set)	3/101 (3.0%)	18/145 (12.4%)	10.05%	13.81%

a. IAS-E data set consisted of all randomized subjects with confirmed UC who received at least 1 dose of blinded study drug in either Study M06-826 or Study M06-827.

Secondary endpoints that are of the binary type will be analyzed using 95% confidence intervals. Comparisons to external placebo will be done as described above. Secondary endpoints that are of the continuous type will be analyzed as changes from baseline, and reported for the two treatment groups including 95% confidence intervals.

Pharmacokinetic:

Adalimumab trough serum concentrations will be summarized by treatment group at each time point using descriptive statistics. In addition, pharmacokinetic model based analyses will be performed with the focus on apparent clearance (CL/F) and apparent volume of distribution (V/F) of adalimumab.

Statistical Methods (Continued):

Immunogenicity:

AAA will be evaluated for each subject and each regimen, and rates of AAA positive will be calculated. As appropriate, the effect of AAA on adalimumab pharmacokinetics, efficacy variable(s), and treatment-emergent adverse events may be evaluated. HACA will be evaluated for each subject and each regimen, and rates of HACA positive will be calculated.

Safety:

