5.0 Analysis Populations

5.1 Definition for Analysis Populations

Seven study populations will be used for analyses in this study. These are:

[figure not shown]
Intent-To-Treat (ITT) population: The ITT population includes all subjects who received at least one dose of the study medication during induction period. ITT subjects will be analyzed as randomized/enrolled.

ITT-E population: The ITT-E population will be a subpopulation of the ITT population, where subjects who have received open-label high induction dose will be excluded. The ITT-E is the primary population for the confirmatory induction period efficacy analyses.

Modified ITT (mITT) population: The mITT population consists of all Week 8 PMS responders who were randomized at Week 8 and received at least one dose of the study medication during maintenance period. mITT subjects will be analyzed as randomized at the beginning of maintenance phase.

mITT-E population: The mITT-E population will be a subpopulation of the mITT population, where subjects who have received Placebo will be excluded. The mITT-E is the primary population for the confirmatory maintenance period efficacy analyses.

Re-Randomized (RR) population: Consists of all subjects who were re-randomized due to a disease flare and received at least one dose of the study medication after the re-

randomization. RR subjects will be analyzed as randomized at the beginning of maintenance phase.

[figure not shown]
Safety population: Includes all subjects who received at least one dose of the study drug. The safety population will be analyzed (separately for induction and maintenance phase) as treated, according to treatment the subject actually received. The safety population will be used for safety analyses.

Per Protocol (PP) populations: The PP populations will only be used for sensitivity analyses of the co-primary and ranked secondary endpoints.

- The I-PP population is a subset of the ITT-E population/mITT-E population consisting of subjects without major protocol deviations within the induction period.
- The M-PP population is a subset of the mITT-E population consisting of subjects without major protocol deviations throughout the study.

The following treatment groups will be distinguished for ITT [ITT-E will comprise only I-HD and I-SD], mITT [mITT-E will comprise only M-HD and M-SD], safety and RR population:

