10.4 Secondary Efficacy Analyses

[figure not shown]
The secondary efficacy endpoints are divided into two groups. The first group consists of ranked secondary efficacy endpoints. The second group includes all other secondary efficacy endpoints and special assessments.

The ranked secondary efficacy endpoints in hierarchical order are:

[figure not shown]
- Proportion of subjects in Mayo clinical response at Week 52 in Week 8 responders per PMS;
- Proportion of subjects who achieve mucosal healing at Week 52 as measured by Mayo endoscopy subscore (defined as ≤ 1) in Week 8 responders per PMS;
- Proportion of subjects who achieve Mayo clinical remission at Week 52 in Week 8 remitters per PMS;
- Proportion of subjects receiving systemic corticosteroids (UC related or non-UC related) at Baseline who have discontinued systemic corticosteroids prior to Week 52* and are in Mayo clinical remission at Week 52 in Week 8 responders per PMS.

Additional exploratory secondary analyses will be performed for:

[figure not shown]
- Proportion of subjects in PMS clinical remission at Week 52 in Week 8 responders per PMS;
- Proportion of subjects in PUCAI remission (defined as < 10) at Week 8;
- Proportion of subjects in PUCAI response (defined as a decrease in PUCAI
 ≥ 20 points from Baseline) at Week 8;

- Proportion of subjects in PUCAI remission (defined as < 10) at Week 52 in Week 8 responders per PMS;
- Proportion of subjects in PUCAI response (defined as a decrease in PUCAI
 ≥ 20 points from Baseline) at Week 52 in Week 8 responders per PMS;
- Proportion of subjects receiving systemic corticosteroids at Baseline who discontinue systemic corticosteroids prior to Week 52* and are in PUCAI remission at Week 52 in Week 8 responders per PMS;
- Change from Baseline in total IMPACT III Quality of Life score and subscores over time for subjects at least 9 years old at Baseline;
- Change from Baseline in WPAI scores over time;
- Change from Baseline in "z" scores for height at Week 26 and Week 52;
- Change from Baseline in BMI at Week 26 and Week 52;
- Change from Baseline in "z" scores for weight-for-age at Week 26 and Week 52;
- Proportion of subjects at appropriate Tanner stage (see Section 6.0) at Baseline, Week 26 and Week 52 (OC analysis);
- Proportion of subjects in PMS response over time;
- Proportion of subjects in PMS remission over time;
- Proportion of subjects in PUCAI response over time;
- Proportion of subjects in PUCAI remission over time;

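### Does the 14.79% external placebo rate for Week 8 remitters rest on studies that had no Week 8 PMS data?

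*SAP*

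**What the plan says.** SAP 10.2, repeated in Protocol 8.1.4.3, names its sources in two adjacent sentences. The first is "Studies M06-826 and M06-827 were the only available data sources with PMS data at Week 8". The second begins "Studies GEMINI 1 and OCTAVE Sustain were the only studies with a similar subject population" and goes on to design and endpoint definitions, as the basis for the Week 52 rates.

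One derivation paragraph then covers Week 52 Mayo remission and mucosal healing in Week 8 responders, "as well as for Mayo Score remission at Week 52 in Week 8 remitters per PMS". All three use GEMINI 1 and OCTAVE Sustain, separate logistic models for anti-TNF naïve and experienced placebo patients, and 0.75/0.25 weights. The constant carried forward is the upper 95% confidence limit of the weighted mean.

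The table gives 18.37% for "Week 52 FMS Remission in Week 8 Responders per PMS" and 14.79% for "Week 52 FMS Remission in Week 8 Remitters per PMS". The second figure is the comparator for ranked secondary endpoint 3 (S3) in SAP 10.4: "Proportion of subjects who achieve Mayo clinical remission at Week 52 in Week 8 remitters per PMS". SAP 5.1 fixes the trial side: "The mITT population consists of all Week 8 PMS responders who were randomized at Week 8". The remitters tested in S3 are therefore a subset of the responders.

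**The concern.** Two things look wrong.

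First, if only M06-826 and M06-827 had Week 8 PMS data, subjects in the other two studies could not have been classified as Week 8 remitters by PMS. Some other, unstated rule would have selected them.

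Second, the order of the two limits is surprising. One would expect subjects already in remission to do at least as well at Week 52 as responders overall. A smaller group also has a wider interval, which pushes its upper limit up. Yet the remitter limit is the lower of the two.

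Together these raise the question whether 14.79% is really a proportion of remitters, or a proportion with a larger denominator such as all responders. S3 is a confirmatory test under familywise error control and 14.79% is its only comparator. If the trial and the external figure used different denominators, the test would not compare like with like.

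**Working it through.** **1. The source sentences.** The second sentence is tied explicitly to the Week 52 endpoints. The paragraphs that follow keep the same split: Week 8 PMS remission uses M06-826 and M06-827, and every Week 52 endpoint uses GEMINI 1, with OCTAVE Sustain where available. Read in place, the first sentence explains the choice of source for the Week 8 endpoint.

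**2. The labels.** All five Week 52 rows are labelled by Week 8 PMS status and come from GEMINI 1 and/or OCTAVE Sustain. The table lists assumptions for this trial's endpoints, so the row names are the trial's endpoint names. The labelling is not peculiar to S3. What is peculiar to S3 is the order 14.79% < 18.37%.

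**3. Checking a limit formula.** No counts are given for the current Week 52 rates, so 14.79% cannot be reproduced. The superseded table in Protocol Appendix O does give counts and is used here only to test the arithmetic. With p the weighted mean and N the total, limit = p + 1.96 × √(p(1−p)/N):

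- Week 8: p = 0.75 × 61/367 + 0.25 × 15/101 = 16.18%, N = 468, limit 19.52%, as printed.
- Week 52: p = 0.75 × 18/145 + 0.25 × 3/101 = 10.05%, N = 246, limit 13.81%, as printed.

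The current Week 8 constant is 19.83%. A logit-scale limit on the old counts gives 19.80%, so the current method is probably closer to that. The simple formula is therefore only approximate for the current table.

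**4. What the two limits imply.** Assume N = 100 to 350 external placebo responders, with a fraction f = 20% to 60% in remission. Neither range is in the documents. Solving the formula for p:

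| Quantity | Range |
|---|---|
| Responders, from 18.37% at N | 12.0% to 14.7% |
| Remitters, from 14.79% at f × N | 5.1% to 10.6% |
| Gap | 4.0 to 6.9 points |
| Other responders, (p_resp − f × p_rem)/(1−f) | 13.7% to 20.7% |
| Odds ratio, remitters against other responders | 0.34 to 0.50 |

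On the logit scale, the corners with 20 to 40 remitters have no solution, and where there is one the remitter rate comes out lower. The ranges show direction and rough size only.

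**5. Could it be chance?** Suppose Week 8 status is unrelated to Week 52 remission. The hypergeometric probability of as few remissions among remitters as step 4 implies runs from 0.7% (N = 350, f = 60%) to 26% (N = 100, f = 20%). This ignores the anti-TNF strata, weights and study effects.

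**6. What S3 requires.** Take 57 × 48/75 ≈ 36 trial remitters, from the planning figures in SAP 4.3, and test at 5% two-sided (the test graph is not shown). With standard error √(0.1479 × 0.8521/36) = 0.0592, 9/36 gives z = 1.73 and 10/36 gives z = 2.20, so success needs 10. Exact one-sided probabilities of reaching 10/36:

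| True placebo rate in remitters | Probability |
|---|---|
| 12.0% | 0.8% |
| 14.7% | 3.1% |
| 14.79% | 3.2% |
| 18.37% | 11.0% |

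If remitters simply share the responder point estimate implied in step 4, S3 behaves acceptably against 14.79%, because that constant is an upper limit and lies above the estimate. The error becomes material only if placebo remitters truly do better than that estimate, for example as well as the responder upper limit.

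**The case for a change.** Even on the endpoint-by-endpoint reading, the plan never states which score and visit defined a responder or a remitter in GEMINI 1 and OCTAVE Sustain, and it gives no counts. The claim of similar endpoint definitions does not fill the gap: the SAP Addendum explains it as Mayo remission at one year, which is the outcome and not the entry condition. Because both constants are upper limits and the remitter group is presumably smaller, the point estimates must differ by more than the 3.58 points between the limits (18.37 − 14.79). A proportion in remission at both visits over all responders would explain the order without remitters doing worse than other responders.

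The missing criterion and the missing counts stand. The suspicion about the denominator does not get further. The SAP and Protocol tables, the derivation text and the endpoint definition all describe remission among remitters, and no passage describes a proportion over all responders. The order can also arise from a real difference, a different mix of the two studies, or chance. Any error rate computed under the all-responder reading would rest on a conjecture the documents do not support, and on assumed sample sizes.

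**Conclusion.** No change to the plan is warranted. The apparent contradiction comes from reading one sentence apart from its neighbour, and the remaining gap is derivation detail that the sponsor must hold, having fitted the models. Naming the external criterion and visit and giving the counts by study and anti-TNF stratum when S3 is reported would settle the matter, without altering the test, its threshold or its power.

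The order 14.79% < 18.37% is unexplained but possible, with a chance probability of up to 26% under the assumptions used. It does not show either figure to be wrong and does not affect the co-primary tests. SAP 12.0 also records the external rates as final and the endpoint analyses as agreed with the agencies.

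This conclusion takes the stated remitter denominator at its word. The sizes quoted rest on 100 to 350 external responders, 20 to 60% of them remitters, about 36 trial remitters and an approximate limit formula. If the counts showed that 14.79% was not a proportion of remitters, S3 would have to be looked at again; nothing in the documents points there.

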10.3 Primary Efficacy Analysis

The co-primary efficacy endpoints are:

- The proportion of subjects who achieve clinical remission at Week 8 as measured by PMS (defined as ≤ 2 and no individual subscore > 1).
- The proportion of subjects who responded at Week 8 per PMS and achieve clinical remission at Week 52 as measured by Mayo score (defined as a Mayo Score ≤ 2 and no individual subscore > 1).

10.4 Secondary Efficacy Analyses

[figure not shown]
The secondary efficacy endpoints are divided into two groups. The first group consists of ranked secondary efficacy endpoints. The second group includes all other secondary efficacy endpoints and special assessments.

The ranked secondary efficacy endpoints in hierarchical order are:

[figure not shown]
- Proportion of subjects in Mayo clinical response at Week 52 in Week 8 responders per PMS;
- Proportion of subjects who achieve mucosal healing at Week 52 as measured by Mayo endoscopy subscore (defined as ≤ 1) in Week 8 responders per PMS;
- Proportion of subjects who achieve Mayo clinical remission at Week 52 in Week 8 remitters per PMS;
- Proportion of subjects receiving systemic corticosteroids (UC related or non-UC related) at Baseline who have discontinued systemic corticosteroids prior to Week 52* and are in Mayo clinical remission at Week 52 in Week 8 responders per PMS.

Additional exploratory secondary analyses will be performed for:

[figure not shown]
- Proportion of subjects in PMS clinical remission at Week 52 in Week 8 responders per PMS;
- Proportion of subjects in PUCAI remission (defined as < 10) at Week 8;
- Proportion of subjects in PUCAI response (defined as a decrease in PUCAI
 ≥ 20 points from Baseline) at Week 8;

- Proportion of subjects in PUCAI remission (defined as < 10) at Week 52 in Week 8 responders per PMS;
- Proportion of subjects in PUCAI response (defined as a decrease in PUCAI
 ≥ 20 points from Baseline) at Week 52 in Week 8 responders per PMS;
- Proportion of subjects receiving systemic corticosteroids at Baseline who discontinue systemic corticosteroids prior to Week 52* and are in PUCAI remission at Week 52 in Week 8 responders per PMS;
- Change from Baseline in total IMPACT III Quality of Life score and subscores over time for subjects at least 9 years old at Baseline;
- Change from Baseline in WPAI scores over time;
- Change from Baseline in "z" scores for height at Week 26 and Week 52;
- Change from Baseline in BMI at Week 26 and Week 52;
- Change from Baseline in "z" scores for weight-for-age at Week 26 and Week 52;
- Proportion of subjects at appropriate Tanner stage (see Section 6.0) at Baseline, Week 26 and Week 52 (OC analysis);
- Proportion of subjects in PMS response over time;
- Proportion of subjects in PMS remission over time;
- Proportion of subjects in PUCAI response over time;
- Proportion of subjects in PUCAI remission over time;
- Change from Baseline in number of daily stool (last non-missing value prior to the respective visit) over time;
- Change from Baseline in albumin and total protein over time;
- Change from Baseline in hemoglobin, hematocrit, red blood cell count over time;
- Change from Baseline in hs-CRP levels over time;
- Proportion of subjects with EIM at Baseline, Week 26 and Week 52 (OC analysis);
- Proportion of subjects with Mayo endoscopy subscore of 0 or 1 (without friability) at Week 52;

[figure not shown]
- Proportion of subjects being hospitalized (all cause) during the study (OC analysis);
- Proportion of subjects being hospitalized (UC-related) during the study (OC analysis);
- Proportion of subjects undergoing colectomy during the study (OC analysis);
- Proportion of subjects receiving systemic corticosteroids at Baseline who have discontinued systemic corticosteroids prior to Week 52* and completed the study (Week 52) (OC analysis);
- Correlation between PMS and PUCAI at different time points;
- Proportion of subjects in a 9 point Mayo (without SFS) clinical remission (defined as ≤ 2 and no individual subscore > 1) at Week 52 in Week 8 responders per PMS;
- Proportion of subjects in a 9 point Mayo (without PGA) clinical remission (defined as ≤ 2 and no individual subscore > 1) at Week 52 in Week 8 responders per PMS;
- Proportion of subjects in a 9 point Mayo (without RBS) clinical remission (defined as ≤ 2 and no individual subscore > 1) at Week 52 in Week 8 responders per PMS;
- Proportion of subjects in a 6 point Mayo (without SFS and endoscopy subscore) clinical remission (defined as ≤ 1) at Week 8;
- Proportion of subjects in a 6 point Mayo (without PGA and endoscopy subscore) clinical remission (defined as ≤ 1) at Week 8;
- Proportion of subjects in a 6 point Mayo (without RBS and endoscopy subscore) clinical remission (defined as ≤ 1) at Week 8;
- Change from Baseline in Mayo score at Week 52;
- Change from Baseline in PMS over time;
- Change from Baseline in PUCAI over time;
- Change from Baseline in endoscopy subscore at Week 52;
- Change from Baseline in SFS over time;
- Change from Baseline in RBS over time;
- Change from Baseline in PGA over time.

*discontinued systemic corticosteroids prior to Week 52: stop date of corticosteroid must be before the min (nominal day of Week 52 per Visit Window table, visit date at which the endpoint was measured).

For the following subset of endpoints, the double-blind high adalimumab dose will be compared to the standard adalimumab dose on the ITT-E (for Week 8 efficacy endpoints) and mITT-E population (for Week 52 efficacy endpoints) in an exploratory manner at an alpha level 0.05 using a two-sample two-sided chi-square test:

- Proportion of subjects in PMS clinical remission at Week 8;
- Proportion of subjects in Mayo clinical remission at Week 52 in Week 8 responders per PMS;
- Proportion of subjects in Mayo clinical response at Week 52 in Week 8 responders per PMS;
- Proportion of subjects who achieve mucosal healing at Week 52 as measured by Mayo endoscopy subscore (defined as ≤ 1) in Week 8 responders per PMS;
- Proportion of subjects receiving systemic corticosteroids at Baseline who discontinue systemic corticosteroids prior to Week 52* and are in Mayo clinical remission at Week 52 in Week 8 responders per PMS;
- Proportion of subjects in PUCAI remission (defined as < 10) at Week 52 in Week 8 responders per PMS;
- Proportion of subjects in PUCAI response (defined as a decrease in PUCAI
 ≥ 20 points from Baseline) at Week 52 in Week 8 responders per PMS;
- Proportion of subjects receiving systemic corticosteroids at Baseline who discontinue systemic corticosteroids prior to Week 52* and are in PUCAI remission at Week 52 in Week 8 responders per PMS;
- Proportion of subjects in PMS clinical remission at Week 52 in Week 8 responders per PMS;
- Proportion of subjects in PUCAI remission at Week 8;
- Proportion of subjects in PUCAI response at Week 8.

*discontinued systemic corticosteroids prior to Week 52: stop date of corticosteroid must be before the min (nominal day of Week 52 per Visit Window table, visit date at which the endpoint was measured).

